Appendix III. Frequently asked questions

Question What should be done if several unique lesions at Measure the longest diameter of the confluent mass and record to add into the sum of baseline become confluent at a follow-up the longest diameters New lesions do not need to meet 'measurability criteria' to be considered valid. If it is How large does a new lesion have to be to count clear on previous images (with the same technique) that a lesion was absent then its definitive appearance implies progression. If there is any doubt (because of the as progression? Does any small subcentimetre lesion qualify, or should the lesion be at least measurable techniques or conditions) then it is suggested that treatment continue until next scheduled assessment when, generally, all should be clear. Either it gets bigger and the date of progression is the date of the first suspicion, or it disappears and one may then it an artefact with the support of the radiologists How should one lesion be measured if on Measure the longest diameter of each lesion and add this into the sum subsequent exams it is split into two Does the definition of progression depend on As per the RECIST 1.1 guideline, progression requires a 20% increase in the sum of the status of all target lesions or only one diameters of all target lesions AND a minimum absolute increase of 5 mm in the sum Are RECIST criteria accepted by regulatory Many cooperative groups and members of pharma were involved in preparing RECIST agencies? 1.0 and have adopted them. The FDA was consulted in their development and supports their use, though they don't require it. The European and Canadian regulatory authorities also participated and the RECIST criteria are now integrated in the European note for guidance for the development of anticancer agents. Many pharmaceutical companies are also using them. RECIST 1.1 was similarly widely distributed before publication RECIST 1.1 recommends that CT scans have a maximum slice thickness of 5 mm and the What is the criterion for a measurable lesion if minimum size for a measurable lesion is twice that: 10 mm (even if slice thickness the CT slice thickness is >5 mm? <5 mm). If scanners with slice thickness >5 mm are used, the minimum lesion size must have a longest diameter twice the actual slice thickness What should we record when target lesions Target lesion measurability is defined at baseline. Thereafter, actual measurements. become so small they are below the 10 mm even if <10 mm, should be recorded. If lesions become very small, some radiologists 'measurable' size? indicate they are 'too small to measure'. This guideline advises that when this occurs, if the lesion is actually still present, a default measurement of 5 mm should be applied. If in fact the radiologist believes the lesion has gone, a default measurement of 0 mm If a patient has several lesions which have Unless the sum meets the PD criteria, the reappearance of a lesion in the setting of PR (or decreased in size to meet PR criteria and one SD) is not PD. The lesion should simply be added into the sum. has actually disappeared, does that patient have If the patients had had a CR, clearly reappearance of an absent lesion would qualify for PD if the 'disappeared' lesion reappears? PD When measuring the longest diameter of target The longest diameter of the lesion should always be measured even if the actual axis is different from the one used to measure the lesion initially (or at different time point lesions in response to treatment, is the same axis that was used initially used subsequently, during follow-up) The only exception to this is lymph nodes: as per RECIST 1.1 the short axis should even if there is a shape change to the lesion that always be followed and as in the case of target lesions, the vector of the short axis may may have produced a new longest diameter? change on follow-up Target lesions have been selected at baseline What may be done in such cases is one of the following: (a) If the patient is still being treated, call the centre to be sure that future evaluations are done with the baseline technique so at least SOME courses are fully evaluable and followed but then one of these target lesions then becomes non-evaluable (i.e. different technique used) (b) If that is not possible, check if there IS a baseline exam by the same technique which What is the effect this has on the other target was used to follow patients...in which case if you retrieve the baseline measures from lesions and the overall response? that technique you retrieve the lesion evaluability (c) If neither (a) nor (b) is possible then it is a judgement call about whether you delete the lesion from all forms or consider the impact of the lesion overall is so important that its being non-evaluable makes the overall response interpretation inevaluable without it. Such a decision should be discussed in a review panel

It is NOT recommended that the lesion be included in baseline sums and then excluded

from follow-up sums since this biases in favour of a response

(continued on next page)

Appendix III - continued

Question Answer

What if a single non-target lesion cannot be reviewed, for whatever reason; does this negate the overall assessment?

Sometimes the major contribution of a single non-target lesion may be in the setting of CR having otherwise been achieved: failure to examine one non-target in that setting will leave you unable to claim CR. It is also possible that the non-target lesion has undergone such substantial progression that it would override the target disease and render patient PD. However, this is very unlikely, especially if the rest of the measurable disease is stable or responding

A patient has a 32% decrease in sum cycle 2, a 28% decrease cycle 4 and a 33% decrease cycle 6. Does confirmation of PR have to take place in sequential scans or is a case like this confirmed PR?

It is not infrequent that tumour shrinkage hovers around the 30% mark. In this case, most would consider PR to have been confirmed looking at this overall case. Had there been two or three non-PR observations between the two time point PR responses, the most conservative approach would be to consider this case SD

In the setting of a breast cancer neoadjuvant study, would mammography not be used to assess lesions? Is CT preferred in this setting?

Neither CT nor mammography are optimal in this setting. MRI is the preferred modality to follow breast lesions in a neoadjuvant setting

A patient has a lesion measurable by clinical exam and by CT scan. Which should be followed?

CT scan. Always follow by imaging if that option exists since it can be reviewed and verified

A lesion which was solid at baseline has become necrotic in the centre. How should this be measured?

The longest diameter of the entire lesion should be followed. Eventually, necrotic lesions which are responding to treatment decrease in size. In reporting the results of trials, you may wish to report on this phenomenon if it is seen frequently since some agents (e.g. angiogenesis inhibitors) may produce this effect

If I am going to use MRI to follow disease, what is minimum size for measurability?

19.5.1 Statistical Model

After study screening procedures, eligible subjects will receive up to 2 i.v. administrations of 177 Lu-3BP-227 in two consecutive treatment cycles 4 weeks apart. A range of doses will be tested, including possibly 2.5, 3, 3.5, 4, 4.5, 5, 5.5, 6, 6.5, 7 and 7.5 GBq per cycle. Additional or alternative dose levels may be chosen. These possible dose levels are labelled as d=1, ..., N, where N is the maximum number of dose levels for the study.

The analysis is based on a method reported by Guede et al.[9] and Tibaldi et al. [37].

If, during Cycle 1, a subject receives dose d_1 and in Cycle 2 dose d_2 , the probability, p, of observing a subject with DLTs up to 4 weeks after the two cycles of dosing is modelled as a function of dose as:

logit
$$(p) = \text{logit } (p_0) + \frac{\text{logit } (33\%) - \text{logit } (p_0)}{MTSA} d_1 + \beta * d_2$$

where p_0 , MTSA and β are the model parameters having the following interpretation:

- p_0 is the probability of observing DLTs under placebo ($d_1=d_2=0$),
- MTSA is the maximum tolerated single activity, being defined as the dose d₁ at which the predicted probability of DLTs is 33% for dosing Cycle 1 (single dose), and
- β is a slope coefficient indicating the impact of a second dose d_2 on DLT probability.

The prior distribution on p_0 , MTSA and β determine the prior distribution on the probability of DLT as a function of up to two doses. For cycle 1 data analysis, the dose d_2 is set to zero. So, only parameters p_0 and MTSA are involved. β is involved when subjects undergo their second cycle. A positive β indicates an increase in DLT probability with second dose.

The MTCA is defined as the maximum tolerated cumulative activity $(d=d_1+d_2)$, where $d_1=d_2$) that may be administered following fractionated i.v. administrations of the same dose d_1 at least 4 weeks apart so that no more than 33% of the subjects experience a DLT during Cycles 1 and/or 2.

The MTCA can be presented as a derived parameter from the logistic regression model. It is expressed as:

$$MTCA = 2* MTSA * \frac{\text{logit } 33\% - logit }{\text{logit } 33\% - \text{logit } p_0 + \beta * MTSA}.$$

The MTCA will be equal to twice the MTSA when β equals 0 (i.e. the DLT probability is not changed after a second dose). When the DLT probability is increased (β >0), the MTCA will be decreased (and vice versa).

During the study, the target organ exposure will be monitored after each dose and doses may be adapted if the exposure exceeds organ-specific maximum acceptability limits. As such, if the predicted MTCA exceeds the maximum acceptability limits for target organ exposure, the maximum radioactivity dose will be used instead. This feature was not considered in the simulation study, where it was assumed that a cumulative dose up to 15 GBq would induce an acceptable organ exposure.

Prior distributions were elicited based on historical knowledge about the placebo DLT rate and the MTSA target. The following prior distributions are used in the trial:

$$p_0 \sim beta(a=1,b=9)$$
,
MTSA $\sim gamma$ (shape = 4, rate = 0.5),
and

 $\beta \sim normal \ (\mu = 0, sd = 0.25).$

Based on these distributions, 20 dose-DLT curves from the prior distribution were simulated after Dose 1 (black) and after Dose 1 and 2 (red) (see Figure 3). The prior probability distributions for the MTSA is summarised in Table 10. The prior probability distributions for the MTCA is summarised in Table 11

[figure not shown]

Figure 3 40 Random Observations (Curves) from the Prior Distribution

Table 10 Prior Probability Distribution of MTSA

Dose range for Cycle 1	Prior MTSA probability
2.5 GBq	5.2%
2.5 to 5 GBq	20.6%
5 to 7.5 GBq	28.6%
>7.5 GBq	45.6%

MTSA=Maximum tolerated single activity.

Table 11 Prior Probability Distribution of MTCA

Dose range (cumulative)	Prior MTCA probability
≤5 GBq	32.5%
5 to 10 GBq	24.6%
10 to 15 GBq	15.7%
>15 GBq	27.2%

MTCA= Maximum tolerated cumulative activity.

Given any set of data, the prior distribution can be updated, yielding a posterior distribution of the parameters. From this posterior distribution many different quantities of relevance can be calculated:

- $E(p|d_1, d_2)$ =Posterior mean probability of DLT for Cycle 1 dose d_1 and Cycle 2 dose d_2 .
- TS_d=(tolerable) Probability that the DLT rate is below 0.33, $Pr(p \le 0.33 | d,0)$, for a Cycle 1 dose d (d₂=0).
- QS_d=Probability of Cycle 1 dose d being the maximum dose where $E(p|d,0) \le 0.33$.
- TC_d=(tolerable) Probability that the DLT rate is below 0.33, $Pr(p \le 0.33 | d/2,d/2)$, for a cumulative dose d (d₁=d₂=d/2).
- QC_d=Probability of cumulative dose d being the maximum dose where E(p|d/2,d/2) <0.33.

Note that, in this model, the MTSA and MTCA are parameters. They have a probability distribution. A consequence of the Bayesian modelling is the probabilities, QS_d , which is the probability that a dose is the MTSA for Cycle 1 and QC_d , which is the probability that a cumulative fractional dose is the MTCA after Cycle 2. This is a powerful question that cannot be answered from a frequentist perspective.

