4.2 Phase I

4.2.1 Dose Escalation

Phase I will consist of a radioactivity escalation part with the objective of determining the MTCA. For phase I, subjects enrolled will have unresectable, locally advanced or metastatic tumours expressing NTSR1 originating from either the pancreas (PDAC), colon and rectum (CRC), stomach (GC), gastrointestinal stromal tumours (GIST), head and neck region (SCCHN) or bone (ES).

The study screening period includes a screening administration of ¹⁷⁷Lu-3BP-227 to assess the tumour uptake of each subject by whole body scan (planar scintigraphy, 1 or 2 timepoint(s) at the investigator's discretion) and optional single photon emission computed tomography (SPECT)/CT scans (up to 2 at the investigator's discretion). Only subjects with a tumour uptake higher than nontumoural surrounding tissue (based on investigator's decision) will be deemed eligible for treatment. The screening period will last 3 weeks but can be extended by up to 2 weeks if this is required for logistical reasons. Subjects who participated in the imaging study, Study D-FR-01087-002, with ¹¹¹In-3BP-227 (also called ¹¹¹In-IPN01087) and who have an uptake of ¹¹¹In-3BP-227 in tumour lesions that is more avid than in the nontumoural surrounding tissue based on whole body imaging (planar scintigraphy), as judged by the investigator, can also be considered for enrolment in this study, provided that they fulfil all other inclusion criteria and do not meet any of the exclusion criteria and were imaged with ¹¹¹In-3BP-227 before the first treatment administration (therapeutic dose) of ¹⁷⁷Lu-3BP-227.

During the treatment phase, it is planned that each subject will receive ¹⁷⁷Lu-3BP-227 fractionated into two i.v. administrations separated by 4 to 5 weeks (+4 weeks in case of reversible AEs) (Figure 1). The safety evaluation will be done over 4 weeks between Cycle 1 and Cycle 2 and over 6 weeks between Cycle 2 and end of core trial (EOCT). During this period, subjects will have repeated imaging for the calculation of individual dosimetry data and will be monitored for signs of toxicity.

Tumour response will be assessed on CT or MRI, as well as with ¹⁸F-FDG-PET scans at the EOCT visit, (corresponding to 6 weeks after the second administration).

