4.2.1.1 Definition of the MTCA

Several radioactivity amounts of ¹⁷⁷Lu-3BP-227 are planned to be tested according to an adaptive radioactivity escalation plan. Each subject will only participate in one part of the protocol. The purpose of the radioactivity escalation part is to determine the MTCA. If not feasible, the maximum tolerated single activity (MTSA) or the maximum administered cumulative activity (MACA) will be determined according to the situation below:

- The MTCA is defined as the maximum tolerated cumulative activity that may be administered following fractionated i.v. administrations of at least 4 weeks apart, so that:
 - No more than 33% of the subjects experience a DLT during Cycles 1 and/or 2 (see DLT definition in Section 4.7.1.1), and
 - The cumulative radiation in each target organ does not exceed the acceptability limits (see Section 4.7.1).
- The MTSA is defined as the highest single radioactivity that can be given so that no more than 33% of the subjects experience a DLT during Cycle 1. The MTSA will be determined in case of unacceptable toxicity seen after Cycle 1.
- The MACA will be determined if the MTCA is not reached during the dose escalation part.

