4.4 Study Endpoints

4.4.1 Primary Endpoint

4.4.1.1 Phase I

For the dose escalation, the primary endpoint is MTCA or MACA, if the MTCA is not identified during the dose escalation part. The primary variables used for the MTCA determination will be the incidence of DLTs (as defined in Section 4.7.1.1) and the organ exposure to radiation during two cycles of treatment. The DLT period for the determination of the primary endpoint

starts at the first administration of ¹⁷⁷Lu-3BP-227 to EOCT/ED. Safety evaluation will encompass DLTs, frequency and nature of AEs, abnormal findings from physical examination, vital signs, 12-lead electrocardiogram (ECG), 3-lead ECG Holter, Eastern Cooperative Oncology Group (ECOG) performance status deterioration, clinical laboratory tests (including haematology, blood biochemistry, hormone analysis, urinalysis and pregnancy test) and changes in specific renal safety biomarkers.

In case the phase I dose expansion cohorts are implemented, the primary endpoint will be safety and tolerability measured by the type, severity, expectedness and frequency of AEs.

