4.4.2 Secondary Endpoints

4.4.2.1 Phase I

For biodistribution and dosimetry of ¹⁷⁷Lu-3BP-227, the secondary endpoints are:

- Maximal uptake (%), maximal concentration achieved (C_{max}); time post injection to achieve maximal concentration (T_{max}); AUC at the target lesions, discernible organs and blood; t_{1/2} of activity concentrations in blood;
- Highest absorbed dose, specific absorbed dose to the target lesions (Gy/GBq), specific absorbed dose per organ (Gy/GBq) and cumulative absorbed organ doses (Gy).

For PK of 3BP-227, the secondary endpoints are:

• PK parameters including, but not limited to, C_{max}, AUC, t_{1/2}, CL, V_d, cumulative amount of unchanged drug excreted into the urine (Ae), renal clearance of the drug from plasma (CL_R), as measured in plasma and urine at defined timepoints.

For pharmacodynamics, the secondary endpoints are:

- Objective response rate and DCR, as determined by RECIST version 1.1 in subjects who received IMP;
- Progression-free survival (PFS) and OS rates as determined from start of study treatment until occurrence of event and/or end of observation period;
- Evaluation of metabolic tumour response using PERCIST (version 1.0) or practical PERCIST;
- Changes in serum tumour markers relevant and specific to the underlying tumour disease from baseline to EOCT, which is planned 6 weeks after the second ¹⁷⁷Lu-3BP-227 dose administration.

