4.7.1.1 Definition of Dose Limiting Toxicity (Dose Escalation)

The DLTs are defined for any of the following IMP-related AEs according to National Cancer Institute - Common Terminology Criteria for Adverse Events (NCI-CTCAE) scale version 5.0 [31], that occur during the defined DLT assessment period (from the first administration of ¹⁷⁷Lu-3BP-227 to EOCT/ED):

- Grade 4 neutropenia for seven or more consecutive days;
- Febrile neutropenia or neutropenic infection (defined as a documented infection with neutrophil count decreased Grade 3 or 4);
- Grade 3 or 4 thrombocytopenia (platelet count decreased) with clinically meaningful bleeding (i.e. requiring urgent hospitalisation or transfusion to manage the bleeding);
- Grade 4 thrombocytopenia for seven or more consecutive days;
- Any Grade 3 anaemia (Hb<8.0 g/dL; transfusion indicated) or Grade 4 anaemia (life-threatening consequences; urgent intervention indicated);
- Any Grade 3 or higher laboratory abnormalities on aspartate aminotransferase/alanine aminotransferase (AST/ALT) with accompanying Grade 2 or higher bilirubin (Hy's law);
- any Grade 3 or higher renal injury/toxicity (estimated glomerular filtration rate (eGFR) <30 mL/min/1.73 m²);
- Any Grade 3 or higher GI AE, not resolved to Grade ≤2 within 48 hours despite optimal adequate medical management, with the following specifications:
 - Grade 3 nausea, vomiting (inadequate oral caloric or fluid intake; tube feeding, total parenteral nutrition or hospitalisation indicated)
 - Grade 3 diarrhoea (increase of ≥7 stools per day over baseline; hospitalisation indicated; severe increase in ostomy output compared to baseline; limiting self-care activities of daily living (ADL)) or Grade 4 diarrhoea (life-threatening consequences; urgent intervention indicated)

- Grade 3 constipation (obstipation with manual evacuation indicated; limiting self-care ADL) or Grade 4 constipation (life-threatening consequences; urgent intervention indicated);
- Any toxicity related to ¹⁷⁷Lu-3BP-227 resulting in a treatment delay of more than four weeks due to either delayed recovery to baseline or resolution of any AE to Grade ≤2 (with the exception of alopecia and lymphopenia).
- Grade 5 toxicity (death)

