12.1 Analysis Sets

For dose escalation only, all subjects who complete Cycle 2 or discontinue during Cycle 1 or Cycle 2 due to a DLT will be included in the MTCA and MTSA evaluations.

For the overall study, all subjects who received at least one dose of the IMP will be included in the safety evaluation. All subjects who receive at least one dose of IMP and who have postbaseline efficacy data will be included in the efficacy evaluations. All subjects with evaluable 3BP-227 PK data and no major protocol deviation with an impact on PK analysis will be included in the evaluation of 3BP-227 PK. All subjects with evaluable dosimetry images and no major protocol deviation with an impact on dosimetry analysis will be included in the evaluation of dosimetry. All subjects with evaluable blood or urine dosimetry data and no major protocol deviation with an impact on ¹⁷⁷Lu-3BP-227 PK analysis will be included in the evaluation of ¹⁷⁷Lu-3BP-227 PK. Major deviations will be described in a specific document.

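### Attachment 5 models DLTs to 4 weeks after dosing, but the protocol's DLT period runs to EOCT/ED; if the shorter window is used, the MTCA would tend to be overestimated

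*Protocol*

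**What the plan says.** - **The model.** Protocol section 19.5.1 takes as its outcome the probability "of observing a subject with DLTs up to 4 weeks after the two cycles of dosing". This is the only place where the modelled p is defined. Section 12.2.4 computes the MTCA and MTSA from the model's parameters.
- **The DLT period.** Section 4.7.1.1 defines DLTs as listed events "that occur during the defined DLT assessment period (from the first administration of" the study drug to EOCT/ED. Section 4.4.1.1 says that the period for determining the primary endpoint "starts at the first administration of ¹⁷⁷Lu-3BP-227 to EOCT/ED".
- **EOCT.** Section 4.2.1 puts the safety evaluation after the second dose "over 6 weeks between Cycle 2 and end of core trial (EOCT"), and section 4.4.2.1 describes EOCT as a visit "which is planned 6 weeks after the second" dose. Table 8 shows it at Day 43, in a column separate from Cycle 2, which ends at Day 29.
- **The MTCA.** Section 4.2.1.1 requires: "No more than 33% of the subjects experience a DLT during Cycles 1 and/or 2".
- **The analysis set.** Section 12.1 sets who enters the MTCA and MTSA evaluations: "all subjects who complete Cycle 2 or discontinue during Cycle 1 or Cycle 2 due to a DLT will be included".
- **The SAP.** Section 3.2.1.1 tabulates DLTs in cycle 1 or 2 and explains that phrase as running from the first administration to EOCT/ED. The SAP does not describe the final Bayesian MTCA model, and its section 5 lists no changes from the protocol.

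**The concern.** The MTCA (or the MACA if no MTCA is found) is the primary endpoint of the dose escalation, and sections 4.3 and 7.1.4.3 make the MTCA the ceiling for phase II activity. The outcome in the model that estimates it has a different time window from the DLT that defines it.

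The two weeks in between can contain events. Haematology and biochemistry are scheduled at Day 43, so Grade 3 anaemia or an eGFR below 30 first found there would be a DLT under section 4.7.1.1. Grade 4 neutropenia or thrombocytopenia that starts on Day 24 or later cannot reach seven consecutive days by Day 29, but can by Day 43.

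No section says how such an event enters the likelihood. Two statisticians could follow these documents and report different MTCAs from the same data. Leaving the late events out lowers the estimated DLT probability at every dose, so the resulting MTCA would tend to be too high.

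**Working it through.** **Step 1: the two windows.** Section 4.2.1.4 places the end of the second cycle at Cycle 2 Day 29. On that reading the model covers 4 of the 6 weeks after dose 2. With a 4-week dose interval it covers 4 + 4 = 8 of the 4 + 6 = 10 weeks from dose 1. The other possible reading, 4 weeks after the end of Cycle 2, gives Day 29 + 28 = Day 57. That lies beyond EOCT and also disagrees with sections 4.4.1.1 and 4.7.1.1.

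**Step 2: even hazard (assumed).** For a dose interval of w weeks, a modelled rate of 33% corresponds to a rate to EOCT of 1 − 0.67^((w+6)/(w+4)). Section 4.2.1 allows 4 to 5 weeks, plus 4 more for reversible AEs, so w runs from 4 to 9.

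- w = 4: 1 − 0.67^(10/8) = 39.4%. Conversely, a true 33% to EOCT appears as 1 − 0.67^(8/10) = 27.4%.
- w = 9: 1 − 0.67^(15/13) = 37.0%. Conversely, 1 − 0.67^(13/15) = 29.3%.

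**Step 3: reproduce the plan's own scenarios.** The model is logit(p) = logit(p0) + [(logit 33% − logit p0)/MTSA]·d1 + β·d2. With L = logit 33% − logit p0, MTCA = 2·MTSA·L/(L + β·MTSA). Section 19.5.3 does not state p0 or β for the scenarios. The values p0 = 5% and β = 0.15, inferred from Table 12, reproduce every scenario B and C entry to within 0.5 percentage points. Then L = −0.708 + 2.944 = 2.236, and:

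- Scenario B (MTSA 14): 28 × 2.236/(2.236 + 2.10) = 14.4 GBq; the plan gives 14 on a 1-GBq grid.
- Scenario C (MTSA 7): 14 × 2.236/(2.236 + 1.05) = 9.5 GBq; the plan gives 9.

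**Step 4: leave out the late DLTs.** Let f be the share of DLTs to EOCT that fall after Day 29 and are not counted. The apparent MTCA then sits where the rate to EOCT is 0.33/(1 − f). The documents give no value for f, so a range is shown.

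| Assumed f | DLT rate to EOCT at apparent MTCA | Scenario C (GBq) | Scenario B (GBq) |
|---|---|---|---|
| 0 | 33% | 9.5 | 14.4 |
| 5% | 35% | 9.9 | 14.9 |
| 10% | 37% | 10.2 | 15.5 |
| 20% | 41% | 11.0 | 16.7 |
| 30% | 47% | 12.1 | 18.3 |

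The even-hazard case with w = 4 (39.4%) gives about 10.7 GBq in scenario C and 16.2 GBq in scenario B. In B the planned two-administration maximum of 15 GBq limits the consequence.

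**The case against.** The strongest reply is that the final estimate is not shown to use the shorter window. Section 12.2.4 words the final model as DLTs in Cycles 1 or 2 with no 4-week cut-off, and the SAP reads the same phrase as running to EOCT/ED. Section 12.2.8 places the full analysis, on the entire dataset, at EOCT. The term DLT itself carries the EOCT/ED window through section 4.7.1.1. Section 12.1 and the rule for when a cohort is complete decide who is included and when; neither censors events. At interim the model is optional, and the SRC reviews all available information. The next cohort may start 3 weeks after the third subject's second dose, before either window closes, so some incomplete follow-up comes from the staggered design whatever 19.5.1 says.

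Most of this stands. A reader might infer that late DLTs are discarded and that the MTCA is biased upward as a matter of fact. The documents do not support that: no section discards events between Day 29 and Day 43.

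The reply does not remove the conflict. The SAP's explanation governs a descriptive table. Section 12.2.4 refers to Attachment 5 for its priors and gives no outcome definition with a different window. That the SRC sees all data does not settle what the model counts.

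**Conclusion.** The inconsistency is real and should be corrected. The bias is conditional: it arises only if the Attachment 5 window is applied literally and some DLTs are first met between Day 29 and Day 43. Its direction would then be towards too high an MTCA.

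Its size cannot be derived from the documents. The figures of 39% and 37% assume an even hazard across both cycles and ignore that subjects with a Cycle 1 DLT receive no second dose. Delayed toxicity would make the gap larger and early toxicity smaller. For an assumed late share of 5% to 30%, the MTCA would rise by about 0.3 to 2.5 GBq in scenario C and 0.5 to 3.8 GBq in scenario B, using inferred scenario parameters and before the 15 GBq limit.

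**What to change.** - In section 19.5.1, define p as the probability of a DLT from the first administration to EOCT/ED.
- Use the same window for the final MTCA/MTSA model in section 12.2.4, carry it into the SAP, and run the final fit on data through EOCT.
- State that each interim fit includes every DLT known at the time and is updated when EOCT data arrive.
- In section 12.1, state that DLTs up to EOCT/ED count for subjects in the MTCA set.

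The cost is a few sentences in the protocol and SAP. Visits, data collection and SRC timing stay as they are. A likelihood weighted by follow-up time is an option for the interim fits. It is not part of the required change, because it is a different method that the Attachment 5 simulations did not evaluate.

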12.2.4 Maximum Tolerated Single and Cumulative Activity

Individual listings and treatment summaries of DLTs with NCI-CTCAE code and grade will be presented.

The incidence of subjects with DLTs during Cycles 1 or 2 will be summarised by treatment and, if possible, modelled as a function of the fractional doses for Cycles 1 and 2 using Bayesian logistic regression. The moderately-informative independent priors used during the interim analysis (see Attachment 5, Section 19.5 for details) as well as noninformative priors will be used for this analysis in order to assess sensitivity of the estimates. Parameter estimates and model predictions will be reported with 90% credibility sets. The MTCA and MTSA will be computed as a derived function of model parameters.

The posterior distribution of the MTCA and MTSA will be summarised in tabular and graphical formats.

The number of subjects with at least one DLT or NCI-CTCAE Grade ≥2 (excluding hair loss) will be tabulated by RL by cycle and overall. The type of DLT and NCI-CTCAE Grade ≥2 will also be presented.

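### The MTCA formula in Attachment 5 gives negative activities where its own definition gives no toxicity limit; Table 11 carries the error, and the planned 90% set is unusable when DLTs are sparse

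*Protocol*

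**What the plan says.** Protocol Section 19.5.1 models the DLT probability p after Cycle 1 dose d1 and Cycle 2 dose d2 as logit p = logit p0 + (A/MTSA)·d1 + β·d2, where A = logit 33% − logit p0. The MTCA is the largest d1 + d2 with d1 = d2, "so that no more than 33% of the subjects experience a DLT during Cycles 1 and/or 2".

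The section then states: "The MTCA can be presented as a derived parameter from the logistic regression model". The expression is MTCA = 2·MTSA·A/(A + β·MTSA). The numerator is read as logit 33% − logit p0, the only reading that gives the stated MTCA = 2·MTSA at β = 0. For β > 0 the text says "the MTCA will be decreased (and vice versa"), so a negative β should raise the MTCA.

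The priors are p0 ~ Beta(1, 9), MTSA ~ Gamma(shape 4, rate 0.5) and β ~ Normal(0, SD 0.25), with no truncation stated. "The prior probability distributions for the MTCA is summarised in Table 11": 32.5% at ≤5 GBq, 24.6% at 5 to 10, 15.7% at 10 to 15 and 27.2% above 15.

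Section 12.2.4 carries the quantity into the final analysis, where DLT modelling is planned if possible: "The MTCA and MTSA will be computed as a derived function of model parameters" and "Parameter estimates and model predictions will be reported with 90% credibility sets". It adds that "noninformative priors will be used for this analysis in order to assess sensitivity of the estimates". SAP Section 3.2.1.1 tabulates DLTs, Section 3.2.25 allows Bayesian modelling at SRC meetings, and Section 5 records no departure from the protocol. Neither document says what to do when the denominator is zero or negative, or when p0 is 33% or more.

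**The concern.** The ratio is the solution of p = 33%. That equals the largest tolerated activity only when p0 is below 33% and risk rises with dose. When β is below −A/MTSA, the combined slope A/MTSA + β is negative. The curve starts below 33% and falls, so every activity is tolerable under the model, yet the formula places the 33% crossing at a negative activity. The value therefore jumps from very large positive to negative just where the definition says there is no limit. This breaks both the verbal definition and the stated direction of the β effect.

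Negative values then sit at the wrong end of the distribution. They inflate the apparent probability that only low activities are tolerable, pull the median down and make the lower credible bound negative. The MTCA is the Phase I primary endpoint when it is identified, and Section 12.2.4 promises its posterior in tables and graphs.

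**Working it through.** **The formula.** Set p = 33% with d1 = d2 = d/2. Then A = (A/MTSA + β)·d/2, so d = 2·MTSA·A/(A + β·MTSA), the protocol's ratio.

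**One draw.** Take p0 and MTSA at their prior means, 10% and 8 GBq.
- A = logit 0.33 − logit 0.10 = −0.708 + 2.197 = 1.489. The ratio changes sign at β = −1.489/8 = −0.186.
- β = −0.15: 2×8×1.489/(1.489 − 1.2) = 23.82/0.289 = 82.4 GBq.
- β = −0.25 (one prior SD below zero): 23.82/(1.489 − 2) = −46.6 GBq. The modelled risk at 2×7.5 GBq has logit −2.197 + (0.1861 − 0.25)×7.5 = −2.676, that is 6.4%.

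**The prior, by simulation (4 to 6 million draws per run).**
- P(ratio < 0) = 18.3%: 17.1 points with p0 < 33%, where the curve never reaches 33%, and 1.2 points with p0 > 33%. P(p0 > 33%) = 0.67^9 = 2.7%.
- Table 11 under different treatments (%):

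| Treatment | ≤5 | 5–10 | 10–15 | >15 GBq |
|---|---|---|---|---|
| Table 11 as printed | 32.5 | 24.6 | 15.7 | 27.2 |
| Ratio, negatives counted as ≤5 | 31.6 | 25.7 | 15.7 | 27.0 |
| Ratio, negatives excluded | 16.3 | 31.5 | 19.2 | 33.0 |
| Ratio, negatives counted as >15 | 13.3 | 25.7 | 15.7 | 45.3 |
| β half-normal | 24.8 | 43.0 | 21.0 | 11.2 |
| Verbal definition, 0 if p0 ≥ 33% | 14.9 | 25.5 | 15.6 | 44.0 |
| Verbal definition, no limit if p0 ≥ 33% and risk falls with dose | 13.4 | 25.5 | 15.6 | 45.5 |

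Only the second row matches the printed table, with every cell within 1.1 points. Negative draws make up 18.3/31.6 = 58% of its ≤5 GBq cell.

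**Posteriors on assumed data.** Five cohorts of three at 2.5, 4, 5.5, 6.5 and 7.5 GBq per cycle, stated priors. The protocol does not give the likelihood, so two constructions were run: two records per subject, at (d, 0) and (d, d), or one record at (d, d). One or two Cycle 2 DLTs are placed at 7.5 GBq per cycle; three means one at 6.5 and two at 7.5. Entries are 5/50/95% points in GBq.

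| DLTs | Records | Negative | Ratio | Verbal definition |
|---|---|---|---|---|
| 1 | two | 8% | −41.4 / 21.1 / 88.7 | 14.1 / 23.2 / above range |
| 1 | one | 22% | −80.3 / 19.0 / 107.5 | 13.2 / 28.3 / above range |
| 2 | two | 1.6% | 11.6 / 16.5 / 38.0 | 12.0 / 16.7 / 46.1 |
| 2 | one | 7.0% | −14.5 / 15.9 / 52.0 | 10.8 / 16.9 / above range |
| 3 | two | 0.4% | 10.5 / 14.2 / 24.7 | 10.6 / 14.3 / 25.4 |
| 3 | one | 2.7% | 8.1 / 13.5 / 30.3 | 9.1 / 13.8 / 45.9 |

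Before rounding, the medians for three DLTs differ by 0.03 to 0.22 GBq. With one DLT, P(MTCA ≤15 GBq) is 17 to 33% by the ratio against 9 to 11% by the verbal definition.

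**Noninformative priors.** Section 12.2.4 gives no values. Assuming an SD for β of 0.5 to 10, other priors unchanged, 29 to 49% of prior draws are negative. With one Cycle 2 DLT, 12 to 36% of posterior draws are negative, and the median is 16.8 to 20.0 GBq by the ratio against 23.5 to 46.0.

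**The case against.** Where p0 is below 33% and the combined slope is positive, the ratio is exactly the verbal definition, so this could be called a missing boundary convention rather than a wrong formula. Its reach is also narrow. Escalation uses QS_d, stopping rules A to D use the MTSA, TS or sample size, and QC_d is defined through p, so none is shown to depend on the ratio. Table 11 describes a prior and drives no stated decision. The final modelling is conditional. The worst intervals arise when the MTCA is hardly identified: with one or two DLTs both medians exceed 15 GBq, and "The MACA will be determined if the MTCA is not reached during the dose escalation part". In Table 13 the median MTCA tracks the truth when it lies in the tested range (14.7 against 14 GBq in scenario B, 9.5 against 9 in C).

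These limits stand and keep the point below a dosing or safety failure. They do not remove it. The region without a rule holds 18.3% of the prior, the printed table reproduces only if that mass is put at the wrong end, and Section 12.2.4 calls for the same function with intervals. The claim about uninterpretable sets needs its limits: it holds for one DLT under both likelihoods, for two DLTs under one of them, and for three under neither.

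**Conclusion.** The concern holds. Taken literally, the formula contradicts the definition beside it for 17.1% of the prior, and Table 11 overstates the probability of an MTCA at or below 5 GBq by about 18 points (32.5 − 14.9 = 17.6). How Table 11 was built is inferred from reproducing it; no section states it. For the final analysis the harm is confined to sparse DLTs: a 90% set with a negative lower bound, a lower median, and P(MTCA ≤15 GBq) 1.5 to 3 times too high with one DLT. It is negligible for the median by three DLTs. The posterior figures rest on the assumed data sets and the two likelihood constructions, and the noninformative figures on assumed SDs for β. Whether the MTCA rows of Table 13 used the ratio is not stated.

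**What to change.** Define the MTCA in Section 19.5.1 from the fitted curve, following the verbal definition:
- A > 0 and A + β·MTSA > 0: the ratio as printed.
- A > 0 and A + β·MTSA ≤ 0: report as above range.
- p0 ≥ 33%: report as 0, and state this as a convention. For draws in which risk then falls with dose, strict use of the words would give no limit; the choice moves Table 11 by 1.5 points.

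Replace Table 11 with the result (14.9/25.5/15.6/44.0% under this convention). Apply the same rule to the posterior and 90% sets in Section 12.2.4, under both informative and noninformative priors, and repeat it in the SAP. In Section 19.5.2, make clear that the MTCA in the Cycle 2 reduction bullet is the same quantity as in the bullet before it. Re-run the MTCA rows of Table 13 only if they used the ratio; that needs the simulation code, whose availability the documents do not show.

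The cost is one definition and one table. No subjects are added, and no prior, escalation rule or stopping rule changes.
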